5.2 EXCLUSION CRITERIA

Subjects who meet any of the following exclusion criteria are not to be enrolled in this trial:

1. Active bacterial, viral, or fungal skin infections.
2. Any noticeable breaks or cracks in the skin on the face, including severely excoriated skin or skin with open or weeping wounds suggestive of an active infection or increased susceptibility to infection.
3. Comorbid skin conditions in the area of application.
4. Active periodontal disease or ongoing procedures (e.g., gum grafting).
5. History/current ocular infections/surgeries within 6 months of enrollment, with the exception of any history of cataracts.
6. History of sarcoidosis.
7. History septic joints/endocarditis.
8. Participants with Netherton's syndrome or other genodermatoses that result in a defective epidermal barrier.
9. Sensitivity to or difficulty tolerating glycerin, polyethylene glycol.
10. History of isotretinoin use, with the exception of sub-therapeutic treatment within 8 weeks of enrollment.
11. Less than 80% compliance with BPO, or less than 5 days' worth of BPO pre-treatment (whichever is greater) during the Screening period.
12. Current major systemic comorbid conditions.
13. Currently participating in (or within 8 weeks of enrollment) another acne trial or other investigational drug.
14. Participants with prosthetic heart valves, pacemakers, intravascular catheters, or other foreign or prosthetic devices/implantable devices/hardware.
15. Participants with close contact (e.g., spouses, children, or members in the same household) with prosthetic heart valves, pacemakers, intravascular catheters, or other foreign or prosthetic devices/implantable devices/hardware.
16. Known chronic human immunodeficiency virus (HIV), hepatitis C virus (HCV), or hepatitis B virus (HBV) infections.
17. History of malignancy (with the exception of non-melanoma skin cancer).
18. Immunosuppression (such as resulting from transplantation, immunosuppressive therapy, active HIV infection/acquired immune deficiency syndrome [AIDS], neutropenia).
19. Major surgical procedure, open biopsy, or significant traumatic injury within 14 days of initiating study drug (unless the wound has healed), or anticipation of the need for major surgery during the study.

20. The presence of a medical or psychiatric condition, history of drug or alcohol abuse that, in the opinion of the PI, makes the subject inappropriate for study inclusion.
21. Participants with close contacts (e.g., spouses, children, or members in the same household) that have severe barrier defects or are immunocompromised.
22. Inability or unwillingness of participant to comply with study protocol procedures.
23. Pregnant or lactating females, or females who desire to become pregnant and/or breast feed within the duration of study participation.
24. Imprisonment or under legal guardianship.

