5.1 INCLUSION CRITERIA

Subjects must meet all the following inclusion criteria to be eligible for participation in the trial:

1. Ability to provide written informed e-consent.
2. Males and Females ages 18-40.
3. Acne severity: Moderate (Grade 3 on 5-point IGA scale and Moderate on an acne lesion count scale (Appendix B [Section 12.2], IGA and Lesion Count Acne Grading).
4. Acne treatment-free period (including topical or oral antibiotics, retinoids, laser therapy, topical dapsone, topical azelaic acid, facial peels, dermabrasion, sulfacetamide sulfur, and salicylic acid), of at least 3 weeks prior to e-consent (with the exception of BPO pre-treatment under this protocol).

5. Lesion count: A minimum of at least a total of 15 inflammatory lesions (papules plus pustules), with a minimum of 10 inflammatory lesions within the designated application area (cheek/nose).
6. Females with non-cyclical acne.
7. Females of childbearing potential willing to use adequate contraception (e.g., total abstinence, intrauterine device (IUD), barrier method with spermicide, surgical sterilization or surgically sterilized partner, Depo-Provera®, Norplant®, or NuvaRing® for the duration of the Screening Period and during study participation. All oral contraceptive and hormonal implants will need to have been initiated and on a stable dose for at least 3 months prior to the screening period. Women of childbearing potential are defined as any female who has experienced menarche and who is NOT permanently sterile or postmenopausal; postmenopausal is defined as 12 consecutive months with no menses without an alternative medical cause.
8. Male participants willing to use an acceptable method of contraception (e.g., total abstinence, barrier methods with spermicide, surgical sterilization or surgically sterilized partner) during study participation.

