5.5 ENROLLMENT PROCEDURES AND TREATMENT ASSIGNMENT

The screening date will be defined as the date the subject signs the ICF. Subjects will be screened within 5 days (+2 days) of enrollment to determine eligibility for participation in the study. Screening laboratory results for hematology (Complete Blood Counts [CBC]) should be obtained from the local laboratory. Screening procedures (Section 8.1) will be performed and documented, at the end of which the clinical site will complete subject and visit information on the Enrollment Request Form (ERF) for Sponsor approval. Approved subjects who meet all inclusion criteria and none of the exclusion criteria may be enrolled into the trial.

It is the responsibility of the PI to ensure that subjects are eligible for the study prior to enrolling into the study. Subjects who do not enroll within the Screening Period will be screen failed. A subject will be considered enrolled once he or she has signed the ICF, met all inclusion/exclusion criteria, executed all screening visit measurements, including daily BPO therapy, and received Sponsor approval to participate.

This is an open-label study. Subjects will be assigned a unique Screening Number at the time of e-consent. Subjects who have met all eligibility criteria will initiate an at-home daily application of a 5.0% BPO gel treatment, and BID Cetaphil® wash and complete an electronic, in-home patient diary (e-diary). They will return to the clinic on Day 1 to perform baseline assessments. Day 1 is defined as the date the first application of NB01 will occur. All baseline tests and procedures must be completed prior to the application of the first dose of study drug on Day 1, time point 0H. Once eligibility is confirmed, subjects will be assigned a unique Subject ID number and be assigned to a cohort. Once a Subject ID has been assigned to a subject, it will not be reassigned to another subject.

Each on-study visit will be scheduled relative to Day 1 0H. Enrolled subjects will complete an in-home e-diary to capture at home Cetaphil® washing through the end of the study. Visits will follow the SOE table and protocol section 8.1. The ERF and additional details can be located in the Study Reference Manual for the trial.

Re-Screening of Subjects

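### Exclusion 10 is worded so that recent sub-therapeutic isotretinoin use is spared, and its two possible readings disagree on who is eligible

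*Combined protocol and SAP*

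**What the plan says.** Exclusion 10 (section 5.2, and word for word in the list in section 2.2) keeps out subjects with a "History of isotretinoin use, with the exception of sub-therapeutic treatment within 8 weeks of enrollment". The documents do not define sub-therapeutic.

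Three other criteria bear on how this is read:

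- Exclusion 13 uses an 8-week window to keep recent exposure out: "Currently participating in (or within 8 weeks of enrollment) another acne trial or other investigational drug".
- Exclusion 5 places a time window before an exception: "History/current ocular infections/surgeries within 6 months of enrollment, with the exception of any history of cataracts". There the window limits the excluded history, and the exception carries no time limit of its own.
- Inclusion 4 requires an "Acne treatment-free period (including topical or oral antibiotics, retinoids, laser therapy" and other listed treatments, "of at least 3 weeks prior to e-consent (with the exception of BPO pre-treatment under this protocol".

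Timing comes from section 5.5. On consent it says "The screening date will be defined as the date the subject signs the ICF", and on the interval "Subjects will be screened within 5 days (+2 days) of enrollment to determine eligibility for participation in the study". A subject counts as enrolled only after having, among other things, "executed all screening visit measurements, including daily BPO therapy, and received Sponsor approval to participate". The Schedule of Events (section 1.2) nevertheless marks Enrollment in the Screening column.

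**The concern.** An exception to an exclusion lets people in. As worded, the people let in are those with the most recent sub-therapeutic exposure, whereas a washout would admit those whose exposure is older. The sentence can also be parsed in two ways, and the two give different answers for the same candidate. Someone whose only isotretinoin use was a therapeutic course a year ago is barred on one parse and admitted on the other.

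The plan treats isotretinoin as important enough for its own exclusion in addition to inclusion 4, so the rule should say what it means. There is no randomization (section 6.3) and no untreated arm, and endpoints are summarized before and after application (section 10.1). If there were any carry-over, no comparison with untreated subjects could separate it from an effect of NB01. With 5 subjects per cohort, one such subject is 1/5 = 20% of a cohort.

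**Working it through.** The protocol states no derived figure to reproduce. The check is day counting on the criteria, with days counted back from enrollment.

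**Inputs**

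- Exclusion 10 window: 8 weeks = 8 × 7 = 56 days before enrollment (section 5.2).
- Inclusion 4: 3 weeks = 21 days before e-consent (section 5.1). I assume that retinoids there include isotretinoin. Section 2.1 supports this by listing oral retinoids among acne therapies.
- E-consent to enrollment: 5 to 7 days (section 5.5). The floor of 5 comes from the minimum of 5 days of BPO (section 1.2, footnote h).
- Alternative: 0 days, if enrollment is counted at Screening as the Schedule of Events column suggests.

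**Two readings of exclusion 10**

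- *A, literal.* The 8 weeks belong to the exception. Any isotretinoin history excludes, unless it was sub-therapeutic and lies within the last 56 days.
- *B, as in exclusion 5.* The 8 weeks belong to the history. Use within 56 days excludes, unless it was sub-therapeutic.

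**Days closed by inclusion 4**

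Closed days = 21 + interval from e-consent to enrollment.

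- 21 + 5 = 26 and 21 + 7 = 28, so the last 26 to 28 days before enrollment are closed.
- With enrollment at Screening: 21 + 0 = 21 days.

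**What remains admissible (day of last use before enrollment)**

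| | Reading A | Reading B |
|---|---|---|
| Sub-therapeutic, day 56 to day 26–28 | admitted, if the whole history lies within 56 days | admitted |
| Sub-therapeutic, day 57 or earlier | barred | admitted |
| Therapeutic, within 56 days | barred | barred |
| Therapeutic, day 57 or earlier | barred | admitted |

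The row admitted on both readings is 56 − 28 = 28 to 56 − 26 = 30 days wide. With enrollment at Screening it is 56 − 21 = 35 days wide. If retinoids in inclusion 4 did not cover isotretinoin, the criteria would leave the window open down to enrollment.

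**Example.** A sub-therapeutic course runs from day 50 to day 42 before enrollment.

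- Exclusion 10: 50 ≤ 56, so the whole course falls inside the exemption on A. On B it is exempt because it was sub-therapeutic.
- Inclusion 4: the last use was 42 − 7 = 35 to 42 − 5 = 37 days before e-consent, and both are at least 21.
- The candidate passes on either reading. The same course taken 6 months earlier is barred on A and admitted on B.

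**Does anything else close the window?** Section 6.3.1 concerns subjects currently taking other acne medication. Section 8.1 records medication from the 2 months before Screening. At 59 to 62 days plus 5 to 7, that reaches 64 to 69 days before enrollment, so it covers day 56, but it records use without barring it. Sponsor approval (section 5.5) is a separate, discretionary step. No written criterion makes these subjects ineligible.

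**The case against.** The best defence is reading B. Exclusion 5 has the same structure, and on that parse the plan is coherent: therapeutic isotretinoin gets an 8-week bar, and sub-therapeutic use falls under the same 3-week rule as the other treatments in inclusion 4. The open window is then simply what a 3-week washout allows, and nothing in the documents shows that 3 weeks is too short.

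The safeguards are also real. Subjects must have moderate acne at entry (section 5.1). IGA and lesion counts are taken at Screening and again on Day 1 before application (section 8.1). The medication record covers the window, the Sponsor reviews each enrollment, and data are tabulated per subject (section 10.4.1). No hypothesis is tested.

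Much of this stands. A reader might infer that exclusion 10 flatly contradicts exclusion 13. That holds only on reading A, because on B both rules bar recent use and exclusion 10 merely adds a carve-out. A reader might also infer that residual isotretinoin would distort tolerability or acne results. The documents give no duration of effect and no count of such subjects, so that is not shown. Nor does either reading admit recent therapeutic use.

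What the defence does not remove is the ambiguity itself. Reading B has to be inferred from a neighbouring criterion, against the literal word order, and the safeguards would identify such a subject without making the subject ineligible.

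**Conclusion.** The point holds as a minor wording defect in an eligibility rule. Taken literally, exclusion 10 runs opposite to a washout. Across its two readings it gives different answers on older sub-therapeutic use and on older therapeutic use. On both readings, sub-therapeutic use from day 56 to about day 26–28 before enrollment is admissible.

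The lower edge rests on two assumptions: that inclusion 4 covers isotretinoin, and that enrollment follows e-consent by 5 to 7 days as section 5.5 describes. Counting enrollment at Screening moves the edge to about day 21 and does not close the window. How many subjects would enter this way, and whether it would affect any endpoint, cannot be derived from the documents.

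**What to change.** Replace exclusion 10 in both section 5.2 and the section 2.2 list. To keep the lifetime bar that the literal text implies:

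*History of isotretinoin use, except sub-therapeutic treatment that ended more than 8 weeks before enrollment.*

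If the sponsor confirms that no lifetime bar is intended:

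*Isotretinoin use within 8 weeks of enrollment.*

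Either wording makes day 57 the latest permitted last use, so the window closes wherever the lower edge falls. If the lifetime-bar sentence is used, the sponsor should also state what counts as sub-therapeutic.

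The cost is one sentence in two places, with no change to visits, sample size or analysis. A rare candidate with recent sub-therapeutic use is lost. Compared with reading A, the lifetime-bar sentence also admits older sub-therapeutic use. Compared with reading B, it also bars older therapeutic use, which could be the larger change in who may enter, so the sponsor should settle the intent before choosing.

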5.3 LIFESTYLE CONSIDERATIONS

Females of childbearing potential need to be willing to use adequate contraception (e.g., total abstinence, IUD, barrier method with spermicide, surgical sterilization or surgically sterilized partner, Depo-Provera®, Norplant®, or NuvaRing® for duration of the Screening period and during study participation. All oral contraceptive and hormonal implants will need to have been initiated and on a stable dose for at least 3 months prior to the screening period. Females must submit to a pregnancy test to ascertain that they are not pregnant before enrolling in the study.

Male participants must be willing to use an acceptable method of contraception (e.g., total abstinence, barrier methods with spermicide, surgical sterilization or surgically sterilized partner) during study participation.

5.4 SCREEN FAILURES

Screening failures are defined as participants who consent to participate in the clinical trial but are not subsequently enrolled to the study intervention or entered in the study within the Screening period. A minimal set of screen failure information is required to be collected to ensure transparent reporting of screen failure participants, to meet the Consolidated Standards of Reporting Trials (CONSORT) publishing requirements and to respond to queries from regulatory authorities. Minimal information includes demography, screen failure details, eligibility criteria, and any AEs.

5.5 ENROLLMENT PROCEDURES AND TREATMENT ASSIGNMENT

The screening date will be defined as the date the subject signs the ICF. Subjects will be screened within 5 days (+2 days) of enrollment to determine eligibility for participation in the study. Screening laboratory results for hematology (Complete Blood Counts [CBC]) should be obtained from the local laboratory. Screening procedures (Section 8.1) will be performed and documented, at the end of which the clinical site will complete subject and visit information on the Enrollment Request Form (ERF) for Sponsor approval. Approved subjects who meet all inclusion criteria and none of the exclusion criteria may be enrolled into the trial.

It is the responsibility of the PI to ensure that subjects are eligible for the study prior to enrolling into the study. Subjects who do not enroll within the Screening Period will be screen failed. A subject will be considered enrolled once he or she has signed the ICF, met all inclusion/exclusion criteria, executed all screening visit measurements, including daily BPO therapy, and received Sponsor approval to participate.

This is an open-label study. Subjects will be assigned a unique Screening Number at the time of e-consent. Subjects who have met all eligibility criteria will initiate an at-home daily application of a 5.0% BPO gel treatment, and BID Cetaphil® wash and complete an electronic, in-home patient diary (e-diary). They will return to the clinic on Day 1 to perform baseline assessments. Day 1 is defined as the date the first application of NB01 will occur. All baseline tests and procedures must be completed prior to the application of the first dose of study drug on Day 1, time point 0H. Once eligibility is confirmed, subjects will be assigned a unique Subject ID number and be assigned to a cohort. Once a Subject ID has been assigned to a subject, it will not be reassigned to another subject.

Each on-study visit will be scheduled relative to Day 1 0H. Enrolled subjects will complete an in-home e-diary to capture at home Cetaphil® washing through the end of the study. Visits will follow the SOE table and protocol section 8.1. The ERF and additional details can be located in the Study Reference Manual for the trial.

Re-Screening of Subjects

Subjects who screen fail may be considered for enrollment at a later date, but must re-sign the ICF and repeat screening procedures, if any screening procedures will be performed outside of the Screening period from the time of the first informed e-consent.

Replacement of Subjects

If a subject is discontinued from the study for any reason other than a dose-limiting toxicity (DLT) prior to completion of the DLT assessment window, a replacement subject will be enrolled at the same dose level as the discontinued subject. To be evaluable for the DLT observation, a subject must receive a dose of NB01 and either completes all safety procedures through Day 7 or experiences a DLT prior to Day 7. It is possible over-enrollment of subjects may occur in order to have 10 safety-evaluable subjects.

6 STUDY INTERVENTION

6.1 STUDY INTERVENTION(S) ADMINISTRATION

6.1.1 DOSING AND ADMINISTRATION

There will be a single application of NB01, at 1 of 2 dose cohorts, administered to approximately 10 subjects:

Once a subject has completed BPO pre-treatment (with an in-home patient e-diary) and been enrolled into the trial, the subject will provide a post-BPO sample immediately prior to receiving their application of NB01 (hereafter referred to as “study drug”). The PI will apply a single dose of NB01 at one of two strengths to each subject at time point 0 hours (0H):

- Cohort 1: Initially, 5 subjects will be enrolled to receive a single topical application of NB01 at 10^5 CFU/cm² to 50 cm² of facial skin covering the nose and cheek. The lower-bound dose determined using the average range of normal bacterial concentration for facial skin (10^5 CFU/cm²).
- Cohort 2: If there are less than 2 DLTs in Cohort 1, then 5 subjects will have a single topical application of NB01 at 10^6 CFU/cm² to 50 cm² of facial skin covering the nose and cheek. The upper-bound dose was determined by upper limit of normal bacterial concentration for facial skin (10^6 CFU/cm²).

Investigators applying the drug shall wash their hands and wear non-powdered nitrile gloves for application of study drug material. Subjects will wash their face with Cetaphil® right after the time point 0H engraftment sample procurement and just before the study drug application. Subjects will document their BID Cetaphil® washing for the remainder of the study.

See Study Assessments and Procedures, for details on pre-and post-visit requirements during the treatment period.

See the Pharmacy Manual for additional study drug handling and management details for this study.

6.2 PREPARATION/HANDLING/STORAGE/ACCOUNTABILITY

6.2.1 ACQUISITION AND ACCOUNTABILITY

NB01 will be supplied frozen to the PI by Naked Biome in single aliquot dosages delivered as a topical solution in a vacuum-sealed cotton applicator pad.

Naked Biome recommends that used study drug supplies be destroyed at sites if they have applicable standard operating procedure (SOP) to do so. If the site has an appropriate SOP for drug destruction as determined by Naked Biome, the site may destroy used (used, partially used or empty) study drug supplies in accordance with that site's approved SOP. A copy of the site's approved SOP will be obtained for central files. If the site does not have an acceptable SOP to destroy, or cannot due to other regulatory reasons, Naked Biome will provide instruction for the return if the used study drug for disposal/destruction. Naked Biome may request return of unused study drug for additional, long-term stability testing.

Investigators will complete product accountability for the over-the-counter products provided to trial subjects (e.g. BPO treatment, Cetaphil® wash). For further details, please see the Pharmacy Manual for this study.

6.2.2 FORMULATION, APPEARANCE, PACKAGING, AND LABELING

The clinical trial formulation comes as a clear solution dispensed using vacuumed cotton pads.

Formulation:

- Live culture of a single strain of *P. acnes*
- Purified water
- Glycerol
- Phosphate buffered saline

All excipients are generally regarded as safe (GRAS) and present in concentrations found in the FDA's Inactive Ingredient Guide <https://www.fda.gov/drugs/informationondrugs/ucm113978.htm>

Formulary breakdown for a 100 ml 25% Glycerol 1X PBS solution:

- Live culture of a single strain of *P. acnes*
- 65 ml Purified water
- 25 ml Glycerol
- 10 ml of 10X Phosphate buffered saline

6.2.3 PRODUCT STORAGE AND STABILITY

Study drug will be stored by the PI in a -80 degrees non-cycling lab freezer before application to study subjects at Day 1. A range of ± 10 degree Celsius is acceptable for storage. Please contact the sponsor in the event of temperature departure from that range. Product must be used within 15 to 30 minutes of removal from lab freezer storage, but is stable for up to 4 hours without significant drop in viability. If for some reason application is not able to occur at the planned visit within 30 minutes, the site will be instructed to discard the product according to the site's sponsor-approved standard operating procedures. Please see the Pharmacy Manual for this study for additional detail.

